5.0 SUBJECT SELECTION AND WITHDRAWAL

5.1 Subject Population

This clinical investigation will enroll male and female subjects who will be undergoing replacement of a native or prosthetic aortic heart valve. Patients must meet all general eligibility criteria and provide written informed consent prior to sites conducting any investigation-specific procedures not considered standard of care.

5.2 Subject Screening and Informed Consent

5.2.1 Subject Pre-Implant Screening

A patient who satisfies all eligibility criteria prior to informed consent will be invited to be enrolled in the clinical investigation.

5.2.2 Informed Consent

The Investigator or his/her authorized designee (if applicable) will conduct the Informed Consent process, as required by applicable regulations and the center's IRB/EC. This process will include a verbal discussion with the patient on all aspects of the clinical investigation that are relevant to the [REDACTED]

Clinical Investigation Plan

patient's decision to participate, such as details of clinical investigation procedures, anticipated benefits, and potential risks of clinical investigation participation. Sites must inform patients about their right to withdraw from the clinical investigation at any time and for any reason without sanction, penalty, or loss of benefits to which the patient is otherwise entitled. Withdrawal from the clinical investigation will not jeopardize their future medical care or relationship with the Investigator.

During the discussion, the Principal Investigator or his/her authorized designee will avoid any improper influence on the patient and will respect the patient's legal rights. Financial incentives will not be given to patients. Patients may be compensated for time and travel directly related to their participation in the clinical investigation. The site shall provide the patient with the Informed Consent Form (ICF) written in a language that is understandable to the patient and that has been approved by the center's IRB/EC. The patient shall have adequate time to review, ask questions, and consider participation. The Principal Investigator or his/her authorized designee will make efforts to ensure that the patient understands the information provided. If the patient agrees to participate, they must sign and date the ICF, along with the person obtaining the consent prior to any clinical investigation-specific procedures. The site will file the signed original copy of Informed Consent Form in the patient's hospital or research charts and provide a copy to the patient.

If study-specific procedures are conducted and/or data were collected from the subject without informed consent, sites should report any failure to obtain informed consent from a patient to the Sponsor within 5 working days and to the reviewing center's IRB/EC according to the IRB's/ EC's reporting requirements.

If, during the clinical investigation, new information becomes available that can significantly affect a subject's future health and medical care, the Principal Investigator or his/her authorized designee (if applicable) will provide this information to the subject. If relevant, sites will ask the subject to confirm their continuing by providing informed consent revision(s) in writing.

5.2.2.1 Special Circumstances for Informed Consent

This clinical investigation excludes individuals unable to make the decision to participate in a clinical investigation on their own or who are unable to fully understand all aspects of the investigation that are relevant to the decision to participate, or who could be manipulated or unduly influenced as a result of a compromised position, expectation of benefits or fear of retaliatory response. This clinical investigation excludes individuals under the age of 18 from the clinical investigation population.

The clinical investigation excludes individuals unable to read or write. The clinical investigation excludes pregnant or breastfeeding women. All other aspects of the Informed Consent process will follow Section **Error! Reference source not found.**

The Investigator or designee, who has been trained on the CIP, will explain the nature and scope of the clinical investigation, potential risks and benefits of participation, and answer questions for the subjects. All subjects (or legally acceptable subjects' representatives, if applicable) must sign and date the IRB/EC-approved Informed Consent form prior to any clinical investigation-specific procedures. Sites may not enroll a patient who is considered part of a vulnerable population in the investigation, except for a member of the armed forces. However, special protection must be given to these patients. When obtaining informed consent from these patients, the physician should be particularly cautious if the patient is in a dependent relationship with the physician or may consent under duress. In that case, an independent witness should be present throughout the Informed Consent process.

Clinical Investigation Plan

5.3 Eligibility Criteria

Assessment for eligibility criteria is based on medical records of the site and an interview with a candidate patient. Patients must meet ALL inclusion criteria to participate in the clinical investigation. If ANY exclusion criteria are met, the patient is excluded from the clinical investigation and cannot be enrolled.

If any clinical and/or laboratory tests are required for patient screening and are not included in a site's standard tests, they must be completed after written informed consent is obtained.

5.3.1 Inclusion Criteria

1. Patient is eligible to be implanted with Regent to replace a native or prosthetic aortic valve per Regent's IFU
2. Subject will be ≥ 18 years of age at time of being consented
3. Subject provides written informed consent prior to any clinical investigation-specific procedure.

5.3.2 Exclusion Criteria

1. Subject is unable to tolerate anticoagulation therapy
2. Subject has active endocarditis
3. Subject is currently participating in another clinical investigation which may interfere with the effectiveness of anticoagulation therapy
4. Pregnant or nursing subjects and those who plan pregnancy during the clinical investigation follow-up period. Women of child-bearing potential must have a documented negative pregnancy test within one week prior to enrollment
5. Subject has anomalous anatomy or medical, surgical, psychological or social history or conditions that, in the Investigator's opinion, could limit the subject's ability to participate in the clinical investigation or to comply with follow-up requirements of the clinical investigation results
6. Subject is unable to read or write or has a mental illness or disability that impairs their ability to provide written informed consent
7. Subject's life expectancy is less than 1 year in the opinion of the Investigator

5.4 Subject Enrollment

A patient is considered enrolled in the clinical investigation from the moment the patient provides written informed consent.

Clinical Investigation Plan

5.5 Subject Withdrawal and Discontinuation

Each subject enrolled shall remain in the clinical investigation until completion of the required follow-up period; however, a subject's participation in any clinical investigation is voluntary, and the subject has the right to withdraw at any time without penalty or loss of benefit. Conceivable reasons for discontinuation may include, but not be limited to, the following:

- Subject death
- Subject did not undergo the Regent MHV implant surgery within 60 days of enrollment
- Subject had an unsuccessful implant of the Regent MHV
- Subject voluntary withdrawal
- Subject lost-to follow-up as described below
- Subject's follow-up is terminated according to Section 3.3

Note: Subjects who undergo a surgical reintervention following the implant of the Regent MHV will not be withdrawn from the study as a consequence of the reintervention. Such subjects will continue follow-up until completing their last scheduled study visit unless withdrawn from the study for another reason.

Sites must notify the Sponsor of the reason(s) for subject discontinuation. Investigators must also report this to their respective IRB/EC as defined by their institution's procedure(s).

No additional follow-up is required or data recorded from subjects once withdrawn from the clinical investigation, except for the status (deceased/alive).

However, if a subject withdraws from the investigation due to problems related to the safety or performance of the device under observation, the Investigator shall ask for the subject's permission to follow his/her status/condition outside of the clinical investigation.

Lost-to-Follow-up

If the subject misses two consecutive scheduled follow-up time points and the attempts at contacting the subject detailed below are unsuccessful, then the subject is considered lost-to-follow-up. Site personnel shall make all reasonable efforts to locate and communicate with the subject (and document these efforts in the source documents), including the following, at each contact time point:

- A minimum of two telephone calls on different days over the specified follow-up windows to contact the subject should be recorded in the source documentation, including date, time and initials of site personnel trying to make contact.
- If these attempts are unsuccessful, the site should send a letter (certified if applicable) to the subject.
- If a subject misses one or more non-consecutive follow-up contact time points, it will be considered a missed visit. The subject may then return for subsequent visits. If the subject misses two consecutive time points and the above-mentioned attempts at communicating with the subject are unsuccessful, the subject will be considered lost-to-follow-up.

Clinical Investigation Plan

Note: Telephone contact with General Practitioner, non-clinical investigation cardiologist, or relative will be considered as subject contact for the purpose of collecting vital status information. The center shall retain records of the contact.

5.6 Number of Subjects

The clinical investigation will enroll 200 eligible implanted subjects. No site may enroll more than 40% of the total subjects. Allowing for subjects who provide written informed consent but are withdrawn without undergoing a Regent MHV implant, RC-PMCF study enrollment is expected to be less than 250 subjects.

5.7 Total Expected Duration of the Clinical Investigation

[REDACTED]

6.0 TREATMENT AND EVALUATION OF ENDPOINTS

6.1 Baseline

The following baseline data will be collected after informed consent is obtained.

- Informed consent process (Section **Error! Reference source not found.**)
- Indication for aortic valve replacement
- Demographics
- Medical history
- Cardiac medications
- Physical examination
- NYHA Classification
- Transesophageal echocardiography (TEE) or transthoracic echocardiography (TTE), per site standard of care

The PI, or delegated study personnel, is responsible for screening potential subjects to determine eligibility for the study. Enrollment information (consent information, inclusion/exclusion information) will be recorded in the subject's medical record and on the Enrollment Case Report Form (CRF). Every effort shall be made to submit the Enrollment CRF within one week of enrollment.

If a subject is consented and undergoes study-specific testing (i.e., testing that otherwise would not be conducted) but does not qualify for the study, the subject will be considered a screen failure and withdrawn from the study.

Clinical Investigation Plan

6.2 Index Procedure

Subjects that meet inclusion and exclusion criteria and provide written informed consent but do not undergo a Regent MHV implant within 60 days of enrollment will be withdrawn without further follow-up required. The following information will be collected during the index procedure.

- Procedure characteristics (e.g., surgeon, access approach, CPB time)
- Regent MHV implant
- Concomitant procedures
- Adverse Events
- Cardiac medications

6.3 Discharge/Post Procedure

The discharge visit will take place prior to hospital discharge or within 7 days after the procedure, whichever occurs first. If the subject is expected to be discharged over the weekend, the visit may be completed on the last weekday prior to discharge.

- Cardiac medications
- International Normalized Ratio (INR) Level (if available)
- Adverse events

6.4 Follow-up Assessments

Required clinical investigation follow-up visits will be performed at the following intervals. The visit window intervals are determined by the date of procedure.

- 3-month visit (90 days \pm 30 days)
- 6-month visit (180 days \pm 30 days)
- 1-year visit (365 days \pm 60 days)
- 2-year visit (731 days \pm 60 days)
- 3-year visit (1096 days \pm 60 days)
- 4-year visit (1461 \pm 60 days)
- 5-year visit (1826 + 60 days)

Follow-up visits can be performed at any point in the window. The subject should be followed at the investigational site where the subject was enrolled and may be followed at another investigational site only with prior agreement from both that site's PI and the Sponsor. All visits and assessments should be completed even if the subject is hospitalized.

During each visit, the following data will be collected:

- Cardiac medications
- TEE or TTE, per site standard of care (6 months and annual visits)
- INR Level

Clinical Investigation Plan

- NYHA Classification (annual visits)
- Adverse events

6.4.1 Follow-up CIP Medications

Antiplatelet/anticoagulation and other medications should be administered per the local institutional standard of care at the investigational site.

6.4.1.1 INR Level Monitoring

INR levels should be maintained per the local institutional standard of care (SOC). INR levels should be recorded per SOC monthly for 3 months after implant. Three months after implant, INR levels should be recorded every 3 months. The site will telephone the subject to obtain INR levels that have been completed as per SOC and record on the INR Log CRF.

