3.0 CLINICAL INVESTIGATION DESIGN

The RC-PMCF is designed to meet the PMCF requirements of the NMPA. This is a prospective, observational, multi-center study of subjects clinically indicated for implantation of a Regent MHV. Two hundred subjects that enroll and undergo surgical aortic valve replacement using a commercially available Regent MHV will participate.

Study enrollment will occur at up to 10 centers in China. The study will enroll subjects expected to be implanted with a Regent MHV who meet all study eligibility requirements. Subjects who do not undergo the Regent MHV implant within 60 days of enrollment will be withdrawn from the study and will not contribute to the study sample size.

Subjects will be followed for 5 years post-implant; [REDACTED]

[figure not shown]
[REDACTED]. Study visits or data collection will occur at baseline, implant, discharge, 3 months, 6 months, and annually through 5 years post-implant.

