6.4.2 Schedule of Events

Table 2 provides a tabulated schedule of the study-required activities and standard of care data collection in the clinical study.

Table 2: Table of Assessments

CIP Activity	Baseline	Procedure (day 0)	Discharge (0-7 days)	3 months (90 ± 30 days)	6 months (180 ± 60 days)	1 year (365 ± 60 days)	2 year (731 ± 60 days)	3 year (1096 ± 60 days)	4 year (1461 ± 60 days)	5 year (1826 + 60 days)
Informed Consent Process	X									
Demographics	X									
Physical Examination	X									
Medical History	X									
Replacement indication	X									
Pregnancy Test	X									
Regent MHV device implant		X								
Concomitant intervention		X								
Procedure Characteristics		X								
TTE or TEE ¹	X				X	X	X	X	X	X

Clinical Investigation Plan

NYHA Functional Classification	X				X	X	X	X	X
Cardiac Medication	X	X	X	X	X	X	X	X	X
INR Level ²			(X)	X	X	X	X	X	X
Adverse Event		(X)							
Deviation		(X)							
Device Deficiency		(X)							
Withdrawal		(X)							
Death		(X)							

(X) – as applicable

¹TTE or TEE should be completed and collected for all cardiac SAEs and device-related AEs

²Site to telephone subject monthly for 3 months post-implant and then every 3 months to collect INR level completed as SOC

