7.3 Adverse Event and Device Deficiency/Device Malfunction Reporting

7.3.1 Adverse Event Reporting

Safety surveillance and reporting starts as soon as the subject is enrolled in the clinical investigation. Adverse events will not be collected for screen failure subjects. Safety surveillance and reporting will continue until sites perform the last follow-up visit, the subject is deceased, the subject concludes participation in the clinical investigation, or the subject withdraws from the clinical investigation. Sites should update additional information regarding an adverse event on the appropriate CRF.

Unchanged, chronic, non-worsening or pre-existing conditions are not AEs and should not be reported.

For the purpose of this trial, the following adverse event types will be reported:

- Adverse events considered related to the implanted Regent MHV
- All serious adverse events

Clinical Investigation Plan

In addition, the following endpoint-related adverse events meeting the Akins²⁵ criteria defined in Appendix II will be reported regardless of seriousness or relatedness:

- Death – all-cause and valve-related mortality
- Reinterventions of the replaced valve
- Major bleeding
- Thromboembolism
- Valve thrombosis
- Endocarditis (operated valve)
- Major paravalvular leak

The Investigator will assess the events for relationship to the device and relationship to the procedure.

The Sponsor will provide an offline form to allow the Investigator to report SAEs in the event the entry cannot be made in the EDC. This does not replace the EDC reporting system. Sites must still enter all information in the EDC system as soon as feasible.

SAE Reporting

The Investigator must report all SAEs to the Sponsor as soon as possible but no later than outlined below.

Clinical Site	Reporting timelines
All Sites	Investigators must report SAEs to the Sponsor no later than 24 hours from the day the site personnel became aware of the event or as per the investigative site's local requirements, if the requirement is more stringent than those outlined.

Sites must record the date the site staff became aware that the event met the criteria of an SAE in the source document. The Investigator will report the SAE to the local IRB/EC according to the institution's IRB/EC reporting requirements.

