8.7 Procedures for Accounting for Missing Data

Every effort will be made to collect all required data. All data available for the endpoints specified among the analysis population will be used. Subjects who do not experience an event will be censored at their last known event-free time point. Descriptive endpoints will be analyzed on the available data without imputation.

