APPENDIX II: DEFINITIONS

The following definitions for primary and descriptive endpoint events will be used in this investigation. These definitions are taken from the Akins *et al.*²⁵ guidelines for adverse event reporting after cardiac valve interventions referenced in ISO 5910:2018 “Cardiovascular implants and extracorporeal systems—Cardiac valve repair devices.” Note that the Akins *et al.* definition of embolism is limited to thromboembolism, which is the term used in the text of the CIP. Similarly, the Akins *et al.* definition of a bleeding event is limited to major bleeding and this terminology is used in the CIP text.

All-cause Mortality: All-cause mortality includes all deaths from any cause after a valve intervention.

Embolism: Embolism is any embolic event that occurs in the absence of infection after the immediate perioperative period. Embolism may be manifested by a neurologic event or a noncerebral embolic event. A neurologic event includes any central, new neurologic deficit, whether temporary or permanent and whether focal or global, that occurs after the patient emerges from anesthesia. A noncerebral embolic event is an embolus documented operatively, at autopsy, or clinically that produces signs or symptoms attributable to complete or partial obstruction of a peripheral artery. Intraoperative myocardial infarctions are not counted. Postoperative myocardial infarction is also not counted unless the infarction is caused by a coronary embolus (as detected by operation, autopsy, or clinical imaging). Emboli consisting of non-thrombotic material (e.g., atherosclerosis, myxoma) are not counted.

Bleeding Event: A bleeding event is any episode of major internal or external bleeding that causes death, hospitalization, or permanent injury (e.g., vision loss) or necessitates transfusion. Major bleeding unexpectedly associated with minor trauma should be reported as a bleeding event, but bleeding associated with major trauma or a major operation should not. Bleeding events are reported for all patients regardless of whether they are taking anticoagulants or antiplatelet drugs. Although total bleeding events must be reported, bleeding events can also be reported separately for those who are taking anticoagulants or antiplatelet agents and those who are not.

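### The recurring INR telephone calls carry no stated event or status question, so between annual visits transient endpoint events may be missed or imprecisely dated

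*Protocol*

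**What the plan says.** Three parts of the plan bear on how endpoint events come to light.

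**Calls.** Protocol 6.4.1.1 states: "The site will telephone the subject to obtain INR levels that have been completed as per SOC and record on the INR Log CRF". Footnote 2 to Table 2 (6.4.2) repeats the purpose and the timing: monthly up to month 3, then quarterly. Neither place attaches a question about events, hospital stays or vital status, and neither gives an end date for the calls.

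**Visits.** Protocol 6.4 introduces its list, which includes adverse events, with "During each visit, the following data will be collected". Visits are at 3 and 6 months and then yearly to year 5. In Table 2 the adverse event and death rows are marked as applicable and are not tied to a time point.

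**Reporting.** Protocol 7.3.1 says "Safety surveillance and reporting starts as soon as the subject is enrolled in the clinical investigation", and it continues until the last visit, death or withdrawal. Serious events are due within 24 hours of site awareness. The listed endpoint events are reportable whether or not they are serious or device-related.

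Two definitions matter. In Appendix II, under embolism: "A neurologic event includes any central, new neurologic deficit, whether temporary or permanent and whether focal or global". In Protocol 8.7: "Subjects who do not experience an event will be censored at their last known event-free time point"; SAP 2.2.3 has the same rule. Neither says whether an INR call establishes that date.

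**The concern.** The site will be speaking to each subject about four times a year, yet the plan has it ask about events at only one of those contacts after year 1. A brief deficit that resolves without admission is the kind of event a subject may not volunteer, and may not date well months later. It still counts toward thromboembolism, one of the rates that Protocol 8.2.3 and SAP 3.5 compare with twice the objective performance criterion (OPC). Under-ascertainment can only move such a rate down, toward a favourable reading, and neither Protocol 8.7 nor SAP 2.8 provides any correction.

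The second issue is the event-free date. If a subject is reached by telephone and later disappears, one programmer could censor reoperation at the last visit and another at the last call. Counting the call without having asked about events would add valve-years in which no one enquired. Not counting it would set aside contact the site did have.

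**Working it through.** The plan states no figure on this point to reproduce. The sample-size reasoning is redacted, and Protocol 8.6 says no formal hypothesis test will be done.

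**1. Number of calls.** Protocol 3.0 says "Subjects will be followed for 5 years post-implant". Assuming the calls run that long, they fall at months 1, 2, 3 and then 6, 9, ..., 60: 3 + 19 = 22. Visit months are 3, 6, 12, 24, 36, 48 and 60, so 22 − 7 = 15 calls fall at no visit month. After month 12 there are 16 calls, 4 of them at visit months, which leaves 12.

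**2. Interval between scheduled enquiries.** Visit days are 365, 731, 1096, 1461 and 1826 (Protocol 6.4).
- Nominal gaps: 366, 365, 365, 365 days.
- Longest gap the windows allow, years 1 to 2: (731 + 60) − (365 − 60) = 791 − 305 = 486 days. The later gaps are at most 485 days.
- Nominal gap if the calls also asked about events: 365.25 / 4 ≈ 91 days.
- Mean delay from event to next enquiry, with events spread evenly: 365.25 / 2 ≈ 183 days now, 365.25 / 8 ≈ 46 days with the calls.

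The like-for-like comparison is nominal with nominal: 365 to 366 days against about 91.

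**3. Possible effect on a rate (illustration).** Inputs: 200 implanted subjects (Protocol 8.3) for 5 years with no attrition give 200 × 5 = 1000 valve-years. The thromboembolism OPC is 1.6% per valve-year, so the comparison value is 2 × 1.6% = 3.2%, or 32 events. Let f be the share of events missed in years 2 to 5. The documents do not give f; it is an assumption, shown from 0 to 30%. With a constant rate, years 2 to 5 hold 80% of the valve-years, so

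observed rate = true rate × [0.2 + 0.8 × (1 − f)].

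| f (assumed) | Factor | Observed rate if true rate is 3.2% | True rate that would read as 3.2% |
|---|---|---|---|
| 0% | 1.00 | 3.20% | 3.20% |
| 10% | 0.92 | 2.94% | 3.48% |
| 20% | 0.84 | 2.69% | 3.81% |
| 30% | 0.76 | 2.43% | 4.21% |

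With a true rate of 4.0% (40 expected events) and Poisson counts, the chance of observing fewer than 32 events is 9% at f = 0, and 19%, 37% and 59% at f = 10%, 20% and 30%.

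**4. Which events are exposed.** Death and reoperation are hard to miss. Under Appendix II a bleeding event requires death, hospitalization, permanent injury or transfusion, and these generally leave records. A temporary neurologic deficit need leave none. The exposure therefore lies mainly in one descriptive rate, and in the censoring date for reoperation.

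**The case against.** The strongest reply is that capture is not confined to visits. Protocol 7.3.1 makes surveillance continuous, Table 2 leaves the adverse event and death rows open, and staff who hear of an event on an INR call must already report it. Protocol 11.4 bases data collection on chart review and so does not rest on recall alone. All of this stands, and it rules out one tempting reading: that events between visits are lost. They may still be volunteered, found in records, or reported with a date at the next visit. The reply does not remove the gap, because the reporting duty and the 24-hour clock begin with awareness, and nothing in the documents prompts anyone to ask between visits.

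A reader might also infer that subjects who disappear are censored at their last visit although the site spoke to them later. The documents do not say so. For valve-related death, a subject who answers the telephone is evidently alive, and Protocol 5.5 accepts telephone contact even with a relative or general practitioner for vital status. Only the reoperation and other event dates are unclear. Part of the primary analysis text is redacted and could address this.

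Three further points stand. The comparison with twice the OPC is descriptive, so no formal decision rule is affected. The case report forms are under separate cover (Appendix VI), so the INR Log may already hold a status prompt. And visit-based enquiry with continuous reporting is a coherent design; the point here is an improvement to it and identifies no contradiction.

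**Conclusion.** The concern holds in a limited form. As written, the calls are for INR only, and scheduled enquiry about events after year 1 is annual, with up to 486 days between enquiries inside the windows. Events that are not volunteered, chiefly temporary neurologic deficits, may be missed or imprecisely dated, and any loss favours the device.

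The size is not known. Under an assumed missed share of 0 to 30% in years 2 to 5, full follow-up and a constant rate, a true 3.2% per valve-year would read as 3.2% down to 2.4%; at a share of zero there is no bias. The call counts of 22 and 15 assume that calls continue to month 60. The primary endpoints are little exposed, apart from the unstated event-free date for reoperation. The change is worth making because the contacts already exist.

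**What to change.** In Protocol 6.4.1.1 and Table 2 footnote 2, add a short fixed script to each INR call:
- vital status;
- any hospitalization;
- any operation or catheter procedure on the valve;
- any bleeding needing treatment or transfusion;
- any new neurological symptom, even if brief.

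Record the answers on the INR Log CRF with the call date and the date of any event, and let any positive answer trigger the adverse event form. State how long the calls continue. In Protocol 8.7 and SAP 2.2.3, say that a completed call with negative answers sets the event-free date used for censoring, so that time at risk and event enquiry advance together.

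Cost: amendment wording, a few form fields and about a minute more per call. No new contact, staff or procedure is needed. The sponsor should expect somewhat more events to document and possibly slightly higher reported rates.
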